### **On-Treatment Period**

The on-treatment period begins at the time of study drug infusion (Hour 0) on Day 1 and ends 72 hours after the end of study drug infusion. The window of 72 hours is based on the half-life of study drug and allows the remaining study drug to clear from the participant's system.

Measurements taken after the time of the initiation of study drug infusion (Hour 0) on Day 1 through the end of study drug infusion plus 72 hours are considered on treatment for all data domains. In addition, if the time of measurement is missing, measurements taken on Day 1 are considered on-treatment for the following data domains: AEs, drug dispensation, exposure, non-study medications.

### **Follow-Up Period**

The follow-up period begins at the end of study drug infusion plus > 72 hours and ends at the Day 180 visit or at the early termination (ET) visit, wherever applicable.

Measurements taken after the end of study drug infusion plus > 72 hours till the end of study for a participant are considered follow-up period for all data domains.

### **3.4. Key Derived Variables**

Imaging data based on on-protocol images per the central review is described in [Appendix 1](#). Imaging-based variables will be derived from the final read per image among on-protocol images (i.e., prior to NSx or CMO or early termination of study drug infusion) from the central review as follows for planned statistical analyses:

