6. STUDY OBJECTIVES AND ENDPOINTS

Primary Objective	Primary Endpoint
To determine if BIIB093 reduces brain contusion expansion by Hour 96 when compared to placebo. Measurements of contusion expansion are based on a comparison of the baseline images and the scans collected prior to and including 96-hour scan, or the scan obtained prior to DC, intraparenchymal hematoma (IPH) evacuation, or comfort measures only (CMO), if earlier.	Change in total contusion volume (hematoma plus perihematomal edema) as measured by brain imaging from baseline to 96 hours or prior to DC, IPH evacuation, or CMO if these procedures occur before 96 hours per the central review.
Secondary Objectives	Secondary Endpoints
To evaluate the effects of BIIB093 on acute neurologic status, functional outcomes, and treatment requirements.	
 • Glasgow Outcome Scale – Extended (GOS-E) at Day 180 • Modified Rankin Scale at Day 90 • Proportion of participants requiring delayed intubation 
Note: delayed intubation is defined as participants requiring intubation (for neurologic deterioration only) at any time between 24 hours and 96 hours postinjury.

To further differentiate the mechanism of action of BIIB093 compared to placebo on contusion expansion by examining differential effects on hematoma and edema expansion.	
 • Change in total contusion volume (hematoma plus perihematomal edema) as measured by brain imaging from baseline to 24 hours or prior to DC, IPH evacuation, or CMO if these procedures occur before 24 hours per the central review. • Change in absolute hematoma volume from baseline to 24 hours • Change in absolute edema volume from baseline to 96 hours

CONFIDENTIAL

The information contained herein may not be used, disclosed, or published without the written consent of
Biogen MA Inc.

To determine if BIIB093 improves survival at Day 90 when compared to placebo.	Time to all-cause death, including neurological death, through Day 90.
[REDACTED]	[REDACTED]
[REDACTED]	[REDACTED] [REDACTED]
[REDACTED]	[REDACTED]
[REDACTED]	[REDACTED] [REDACTED] [REDACTED] [REDACTED] [REDACTED] [REDACTED] [REDACTED]
[REDACTED]	[REDACTED]
[REDACTED]	[REDACTED]

CONFIDENTIAL

The information contained herein may not be used, disclosed, or published without the written consent of
Biogen MA Inc.

[REDACTED]	[REDACTED]

CONFIDENTIAL

The information contained herein may not be used, disclosed, or published without the written consent of

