16.2. Efficacy

16.2.1. Analysis Population

The primary efficacy analyses will be conducted in the modified intent-to-treat population, which is defined as participants who are randomized and treated and have at least 1 centralized read of contusion volume from an NCCT or MRI scan acquired between 12 hours after the initiation of study treatment and by the Hour 96 Visit or prior to DC, IPH evacuation, or CMO, if performed before the Hour 96 visit.

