#### **3.4.1. Change in Total Contusion Volume (hematoma plus perihematomal edema) from Baseline to 96 Hours**

Total contusion volume will be assessed by the central imaging core laboratory on baseline NCCT, 24-hour NCCT, and the 96-hour scan (MRI and / or NCCT) and the scans obtained prior to DC, IPH evacuation or CMO. Change in total contusion volume (hematoma plus perihematomal edema) as measured by brain imaging from baseline to 96 hours or prior to DC, IPH evacuation, or CMO if these procedures occur before 96 hours per central review, will be derived from available central reads, at baseline (before Hour 0) and closest to Hour 96. If multiple timepoints

are applicable, the read from the visit closer to Hour 96 will be used for analysis. If both MRI and NCCT have been carried out then the MRI read will be used.

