### 3.6.1. Full Analysis Set

The full analysis set, i.e., the modified intention-to-treat (mITT) participants, will include all the participants who are randomized, receive any study drug (BIIB093 3 mg/day, BIIB093 5 mg/day or the matching placebo), and have at least one final read per central review of contusion volume from an NCCT or MRI scan acquired between 10 hours after the initiation of study drug infusion and the Hour 96 visit or NSx or CMO (if earlier). In efficacy analyses performed on the full analysis set (mITT participants), participants will be analyzed according to the randomized treatment group (see [Section 3.2.1](#) for the definition).

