### 5.5.3. Non-drug Therapies

A concomitant therapy (including medication or non-drug therapy) is defined as any therapy that is taken on or after the start date/time of study drug infusion. This includes therapies that are started prior to start of study drug infusion if their use continues after study drug infusion. If a participant never receives study drug, date of randomization will be used, if applicable. Handling of partial or missing start/stop date/time is described in [Section 5.1](#). Concomitant non-drug therapies will be coded using MedDRA.

The following non-drug therapies will be summarized by randomized treatment group and total and by indication for mITT participants:

- Number (%) of participants taking any non-drug therapies.
- Number (%) of participants requiring NSx including craniotomy and DC, time and the reasons of DC.
- Number (%) of participants with decision of CMO, time and reasons of CMO.
- Number (%) of participants requiring delayed intubation, time and reasons of delayed intubation.

A listing of non-drug therapies for randomized participants will be provided.

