### 5.6.2. Primary Efficacy Endpoint

Primary endpoint is the change in total contusion volume (hematoma plus perihematomal edema) as measured by brain imaging from baseline to 96 hours or prior to DC, IPH evacuation or CMO if these procedures occur before 96 hours per the central review. The definition of main estimand follows a white-on-treatment strategy [ICH E9 (R1) Addendum, 2020], i.e., all the central reads between 12 hours after the initiation of study drug infusion and Hour 96 or prior to DC, IPH evacuation or CMO if these procedures occur before 96 hours will be used; see details in Section [3.4.1](#).

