## **APPENDICES**

## APPENDIX 1. IMAGING DATA PER THE CENTRAL REVIEW

### *On-Protocol Images for the Central Review*

MR and NCCT images will be used to assess changes in brain contusion, hemorrhage and edema volume, [REDACTED]. Eligible participants will undergo NCCT at baseline and Hour 24 and MRI/NCCT at Hour 96.

- Screening NCCT will be the one closest to the randomization, which is assessed for eligibility with a brain contusion volume of > 3mL per investigator review and used for stratification at randomization
- All NCCT/MRI brain images collected by the imaging CRO up to the Hour 96 visit (or NSx or CMO, if earlier) will be considered on-protocol images and will be submitted for central review

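### Three different image cut-offs are in force: SAP 3.4 and 3.6.1 exclude scans, and sometimes participants, that the protocol's primary endpoint and mITT definition keep

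*SAP*

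**What the plan says.** Three rules decide which scans can feed the primary endpoint.

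- **Rule A, SAP 3.4.** The lead-in to all imaging-derived variables limits them to "on-protocol images (i.e., prior to NSx or CMO or early termination of study drug infusion"). The pool closes at any NSx, at CMO, or when the infusion ends early.
- **Rule B, SAP 3.6.1 and Appendix 1.** The full analysis set needs a central read from a scan taken between 10 hours after infusion start "and the Hour 96 visit or NSx or CMO (if earlier"). Appendix 1 says that images collected "up to the Hour 96 visit (or NSx or CMO, if earlier) will be considered on-protocol images" and go to central review. Neither mentions an infusion stop.
- **Rule C, the protocol and the specific SAP definitions.** Protocol section 6 measures change to 96 hours or "prior to DC, IPH evacuation, or CMO if these procedures occur before 96 hours per the central review". Protocol 16.2.1 defines the mITT population by a scan up to the Hour 96 visit or "prior to DC, IPH evacuation, or CMO, if performed before the Hour 96 visit". SAP 3.4.1 repeats the same three events: "CMO if these procedures occur before 96 hours per central review, will be derived from available central reads". SAP 5.6.2 says that reads up to Hour 96 or "prior to DC, IPH evacuation or CMO if these procedures occur before 96 hours will be used".

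Two further passages bear on the infusion stop. SAP 5.6.2 labels the main estimand white-on-treatment, evidently meaning while-on-treatment. SAP 3.3 treats measurements up to 72 hours after the end of infusion as on treatment. SAP section 6 lists no change from the protocol's analyses.

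**The concern.** The choice of scan is the primary endpoint here. If the pool of admissible scans depends on which SAP section a programmer follows, two people working from the same document can build different primary datasets.

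The events that separate the rules, other NSx and early infusion stop, occur after randomization and may be related to treatment or to prognosis. Removing scans or participants because of them departs from the protocol endpoint and could distort the comparison. The protocol endpoint also truncates at post-randomization events, so the question is not whether truncation is allowed but which events trigger it. On that the documents disagree, and the SAP does not say that it has changed anything.

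**Working it through.** No arithmetic settles this, and the sample-size calculation is not in question. The check sets the passages side by side.

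**1. Is NSx really wider than DC plus IPH evacuation?** Yes. Footnote 5 to protocol Table 2 separates IPH evacuation, DC and CMO from other NSx, for which no scan is expected. Protocol 11.4.2.1 covers extra-axial evacuation and ventricular drains under the NSx heading. SAP 5.5.3 tabulates "Number (%) of participants requiring NSx including craniotomy and DC, time and the reasons of DC". Exclusion criterion 2 bars only an indication for immediate IPH evacuation or DC, so someone who needs extra-axial surgery can be enrolled.

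**2. Can a later scan exist?** Yes. Protocol 11.4.2.1 continues study treatment and normal follow-up after NSx. Protocol 10.1 encourages participants who stop treatment to continue the required assessments.

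**3. Apply each rule to constructed cases, each with scans at Hours 24 and 96.**

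| Case | Rule A | Rule B | Rule C |
|---|---|---|---|
| 1. Infusion stops at Hour 30 | Hour 24 scan only | Both scans | Both scans; Hour 96 is the endpoint |
| 2. Extra-axial craniotomy at Hour 8, infusion completed | No post-baseline scan | No post-baseline scan; outside the full analysis set | Both scans; in the mITT population |
| 3. Infusion stops at Hour 8 | No post-baseline scan | Both scans; in the full analysis set | Both scans; Hour 96 is the endpoint |
| 4. Infusion completed, no NSx or CMO | Both scans | Both scans | Both scans |

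The rules also agree when the only event is DC, IPH evacuation or CMO. In case 3 the SAP contradicts itself: 3.6.1 admits the participant and 3.4 leaves nothing to analyze.

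**4. Does the while-on-treatment idea justify a cut at the infusion stop?** The definition given in SAP 5.6.2 names only DC, IPH evacuation and CMO. Under SAP 3.3 the on-treatment period in case 1 runs to Hour 30 + 72 = Hour 102, so the Hour 96 scan is on treatment, yet Rule A excludes it. In case 3 it runs to Hour 8 + 72 = Hour 80. The Hour 24 scan is then on treatment, and Rule A excludes that too. Neither passage gives a cut at the stop itself.

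**5. What value would a case 1 participant have under Rule A?** SAP Table 1 maps the Hour 24 scan to the window [10, 38], not to [76, 116], which would leave Hour 96 missing. SAP 3.4.1 takes the available read nearest Hour 96, which could substitute the Hour 24 read. The SAP does not say which applies.

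**6. Does a listed analysis cover the gap?** SAP 5.6.2 lists three: excluding DC, IPH evacuation and CMO; the per-protocol set; and eCRF covariates. None varies the image cut-off.

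**The case against.** The strongest reply is that the specific text governs the general. The primary variable is stated the same way in the protocol, SAP 2.1, SAP 3.4.1 and SAP 5.6.2, and 5.6.2 refers the reader to 3.4.1. The clause in 3.4 is only a parenthesis in a lead-in. On that reading case 1 resolves to the protocol version.

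This has some force for the infusion stop, but it does not cure the conflict. Section 3.4 sets the pool from which 3.4.1 draws. Appendix 1 describes only pre-NSx images as going to central review, so a post-NSx Hour 96 scan may have no read for 3.4.1 to use. Section 3.6.1 is itself the specific definition of the analysis set, so case 2 remains.

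A second reply is that while-on-treatment explains the infusion-stop clause. It may well be where the clause came from, but step 4 shows that neither the definition in 5.6.2 nor the window in 3.3 supports it.

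A third is that the per-protocol set removes infusions stopped within 12 hours. That covers case 3 in a secondary analysis, but not later stops or other NSx. It also implies that the SAP expects early stoppers in the main set.

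It stands that detailed reading procedures sit in the Imaging Manual and reading guidelines, which are not available here. They could settle which scans are actually read, but they would not remove the contradiction in the SAP.

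**Conclusion.** The conflict is real and should be fixed. For participants with another NSx or an early infusion stop before the Hour 96 scan, SAP 3.4 and 3.6.1 as written exclude scans, and sometimes participants, that the protocol's endpoint and mITT definition include, with no declared change. This rests on the text alone and confidence in it is high.

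Its size cannot be determined: the documents give no rate of early infusion stop or of other NSx.

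A reader might infer more than the documents support:

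- **That the endpoint is undefined generally.** It is not. All rules agree for participants with a completed infusion and no other NSx.
- **That affected participants are missing at Hour 96.** Table 1 suggests this, but the nearest-read rule in 3.4.1 allows substitution, so it is unclear.
- **That the result is biased, or power materially reduced.** Neither the direction nor the amount of bias can be worked out. A power figure would rest on an invented number of lost scans and would say nothing about selective exclusion.

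The NSx wording resembles the superseded Version 2 text shown in the amendment summary, so a carry-over is likely, but that is an inference.

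**What to change.** Before the Day 4 lock:

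1. Use DC, IPH evacuation or CMO as the only image cut-off in SAP 3.4, 3.6.1 and Appendix 1, matching protocol sections 6 and 16.2.1 and SAP 3.4.1 and 5.6.2.
2. Delete the infusion-stop clause from 3.4.
3. Reword the estimand label in 5.6.2 to say that images are truncated only at those three events and not at an early infusion stop. Removing the clause while keeping the while-on-treatment label would leave a new contradiction.
4. Report the version cut at infusion stop or any NSx as a supplementary analysis. State whether a participant whose later scans are cut is missing at Hour 96 or takes the nearest earlier read.

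If the sponsor intends the narrower cut for the main analysis, declare it in SAP section 6 and 5.6.2, align the other sections, and report the protocol version as a sensitivity analysis.

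The cost is SAP wording, one derivation rule and possibly central reads of post-NSx scans. Protocol 19.1.5 already sends those scans to the imaging core laboratory, so no new visits or scans are needed.

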#### **3.4.1. Change in Total Contusion Volume (hematoma plus perihematomal edema) from Baseline to 96 Hours**

Total contusion volume will be assessed by the central imaging core laboratory on baseline NCCT, 24-hour NCCT, and the 96-hour scan (MRI and / or NCCT) and the scans obtained prior to DC, IPH evacuation or CMO. Change in total contusion volume (hematoma plus perihematomal edema) as measured by brain imaging from baseline to 96 hours or prior to DC, IPH evacuation, or CMO if these procedures occur before 96 hours per central review, will be derived from available central reads, at baseline (before Hour 0) and closest to Hour 96. If multiple timepoints

are applicable, the read from the visit closer to Hour 96 will be used for analysis. If both MRI and NCCT have been carried out then the MRI read will be used.

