16.2.2.2. Analysis of the Primary Endpoint

Primary analysis of the primary endpoint will compare BIIB093 (3 mg/day or 5 mg/day) and placebo groups using an ANCOVA (analysis of covariance) model, adjusting for covariates including all the stratification factors at randomization, 96 hours imaging modality (MRI vs NCCT) and baseline contusion volume per the central read. Multiple imputation will be used to account for the missing values for Hour 96.

Sensitivity analyses for the assumptions will be performed to evaluate the impact of analysis sets, the impact of missing data, and the intercurrent event handling. Details will be specified in the SAP.

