Change in absolute edema volume from baseline to 96 hours

ANCOVA will be performed to compare the mean change from baseline between BIIB093 (3 mg/day or 5 mg/day) and placebo groups. This endpoint will be evaluated for all participants having a scan acquired between 12 hours after the initiation of study treatment and the Hour 96 Visit. Multiple imputation will be used to account for missing values for the Hour 96. Summary statistics, including by-visit number of participants with data, mean, SD, median, quartiles, and range will be provided.

Time to all-cause death, including neurological death, through Day 90

Survival time will be analyzed for all randomized participants. Cox proportional hazards regression models will be used to assess the treatment effects on overall survival at Day 90 after adjusting for covariates including the stratification factors at randomization, baseline contusion volume per the central review, and baseline GCS. Kaplan-Meier curves will be presented for BIIB093 (3 mg/day or 5 mg/day) and placebo groups.

CONFIDENTIAL

The information contained herein may not be used, disclosed, or published without the written consent of Biogen MA Inc.

[REDACTED]

[REDACTED]

[REDACTED]

[REDACTED]

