## 1. Introduction

This statistical analysis plan (SAP) provides details of all pre-planned statistical analyses for Study 252BN201 (protocol version 3.0). Any deviation to this SAP will be described in the Clinical Study Report (CSR).

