#### 5.1.4. Missing Values for GOS-E

GOS-E at [REDACTED] 180 will be analyzed as a 7-category ordinal scale (1/2, 3, 4, 5, 6, 7, 8). Multiple imputation will be used to account for missing values for GOS-E. Death and vegetative state are scored as 1 and 2 in GOS-E and therefore no missing GOS-E values are expected due to death or vegetative state. Missing GOS-E values due to reasons other than death or vegetative state will be imputed based on a linear model performed on the GOS-E scores leveraging the information of the patient at other time points as well as the time patterns of all other participants. The model will include treatment as a classification variable and other covariates: GOS-E score at the previous timepoint, region (North America and RoW), age ( $\leq 70$ ,  $> 70$  years), baseline GCS (5-8, 9-12, 13-15), baseline contusion volume per investigator ( $> 3$  to 10 mL vs  $> 10$  mL). Imputed values will be rounded to the closest valid GOS-E score, 100 imputations will be conducted with random seed pre-specified, and each imputation will result in a complete dataset for all mITT participants.

The missing data pattern will be evaluated including reasons for missingness, missing data by randomized treatment group and visit, and potential covariates associated with missingness. Sensitivity analyses will be planned to evaluate the robustness of the results from the main analysis of GOS-E.

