To explore the exposure-response relation of different BIIB093 doses, similar efficacy endpoint models will be used for analyzing the two active dose arms separately (BIIB093 3 mg/day vs. BIIB093 5 mg/day vs. placebo). The results of the exposure-response analysis will report point estimate of the treatment effect (odds ratio, hazard ratio, or least-square mean difference) and the corresponding 2-sided 95% CIs. No p-values for the exposure-response analysis will be reported.

Table 3: Main Analyses for Efficacy Endpoints

Endpoints	Analysis method	Analysis Population	SAP Section
Primary endpoint			
Change in total contusion volume as measured by brain imaging from baseline to 96 hours or prior to DC, IPH evacuation or CMO if these procedures occur before 96 hours per the central review	Analysis of Variance (ANCOVA)	mITT per-protocol	5.6.2

Secondary endpoints			
GOS-E at Day 180	Ordinal logistic regression with multiple imputation	mITT per-protocol	5.6.3
mRS as 5-category ordinal scale (0/1, 2, 3, 4, 5/6) at Day 90	Ordinal logistic regression	mITT per-protocol	5.6.3
mRS as 2-category ordinal scale (0-2 vs 3-6) at Day 90	Binary logistic regression	mITT per-protocol	5.6.3
Proportion of participants requiring delayed intubation	Binary logistic regression	mITT per-protocol	5.6.3
Change in total contusion volume from baseline to 24 hours or prior to DC, IPH evacuation or CMO if these procedures occur before 24 hours per the central review	Analysis of Variance (ANCOVA)	mITT per-protocol	5.6.3
Change in absolute hematoma volume from baseline to 24 hours	Analysis of Variance (ANCOVA)	mITT per-protocol	5.6.3
Change in absolute edema volume from baseline to 96 hours	Analysis of Variance (ANCOVA)	mITT per-protocol	5.6.3
Time to all-cause death through day 90	Cox proportional hazards regression model	mITT per-protocol	5.6.3

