### Main Analysis

The analysis of the primary endpoint will consist in testing the null hypothesis  $H_0: p_1 = p_2$  versus the alternative hypothesis  $H_1: p_1 \neq p_2$ , where  $p_1$  is the change from baseline of total contusion volume in the placebo group and  $p_2$  that in the BIIB093 combined group according to the randomized treatment group for the full analysis set.

- The hypothesis will be tested using ANCOVA, adjusted for covariates specified in Section [5.6.1](#), at a 2-sided significance level of 0.05 with the Day 4 database.
- The estimated least squared mean difference for treatment group, the corresponding 95% confidence interval and the p-value will be reported.
- In case that the ANCOVA does not converge numerically due to perfect separation of the responses by some stratification factor, the stratification factor that causes it will be excluded from the model.

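### The SAP drops, without declaring it, the protocol's multiple imputation for missing Hour 96 contusion and edema volume, and gives two conflicting rules for what counts as an Hour 96 value

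*SAP*

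**What the plan says.** **Protocol.** For the primary endpoint, section 16.2.2.2 states: "Multiple imputation will be used to account for the missing values for Hour 96". It adds that sensitivity analyses "will be performed to evaluate the impact of analysis sets, the impact of missing data, and the intercurrent event handling", with details left to the SAP. For the edema endpoint, section 16.2.2.3 states: "Multiple imputation will be used to account for missing values for the Hour 96".

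**SAP, missing data.** Section 1 says the SAP covers all planned analyses under protocol version 3.0. Section 5.1.4 states: "Multiple imputation will be used to account for missing values for GOS-E". In Table 3 only the GOS-E row names imputation ("Ordinal logistic regression with multiple imputation"). For the primary endpoint, the main analysis in 5.6.2 says "The hypothesis will be tested using ANCOVA, adjusted for covariates specified in Section" 5.6.1, and neither section contains an imputation step. Edema change is analysed on observed data (5.6.3). The sensitivity and supplementary list in 5.6.2 covers exclusion of procedures, the per-protocol set and eCRF covariates, but not missing data. Section 6, on changes from the protocol, is marked not applicable.

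**SAP, scan choice.** Section 3.4.1 says the change "will be derived from available central reads, at baseline (before Hour 0) and closest to Hour 96" and states no window. Section 5.6.2 admits all central reads from 12 h after the start of infusion and refers to 3.4.1 for detail. Table 1, in section 3.1, gives volume data an Hour 96 window of [76, 116] h and an Hour 24 window of [10, 38] h. Edema is taken from the visit chosen for total contusion volume (3.4.4).

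**The concern.** The primary analysis and one secondary analysis would be run by a method that the protocol does not state, with nothing in the SAP to tell the reader so. For edema the SAP states the opposite of the protocol.

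The two scan rules add a second problem. Take a participant with a 24-hour scan, no 96-hour scan, and no decompressive craniectomy (DC), intraparenchymal hematoma (IPH) evacuation or comfort measures only (CMO). Under Table 1 this participant has no Hour 96 value, and nothing says what happens next. Under 3.4.1 with 5.6.2, the 24-hour change becomes the 96-hour outcome. The treatment contrast is then a blend of 24-hour and 96-hour effects, although protocol 4.5.1.3 expects contusion progression and edema as late as 3 to 4 days after injury. No planned sensitivity analysis tests either handling.

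**Working it through.** **1. Does either SAP reading deliver the protocol's analysis?** Consider the participant described above.

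| Source | Hour 96 value | Next step |
|---|---|---|
| Protocol 16.2.2.2, 16.2.2.3 | Missing | Multiple imputation |
| SAP Table 1 | Missing (24 h lies outside 76 to 116 h) | None stated |
| SAP 3.4.1 with 5.6.2 | The 24-hour read | ANCOVA |

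The protocol also places the 96-hour scan within 18 hours of Hour 96 (Table 2, footnote 15), so not before 96 − 18 = 78 h. Neither SAP row matches the protocol row.

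**2. The plan's own power figure.** Inputs from protocol 16.8 and SAP 2.3: difference 15 mL, SD 29 mL, 80 per pooled group, two-sided 5%. SE = 29 × √(2/80) = 4.585 mL and 15/4.585 = 3.27. The noncentral t with 158 df gives power 0.902, so the stated figure of about 90% reproduces. It counts all 80 per group as evaluable.

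**3. Illustration.** The documents give no rate of missing Hour 96 scans and no 24-hour effect. Assume a fraction f missing equally in both groups, with f = 0.10 or 0.20.

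- *Cases dropped.* n = 80(1 − f) = 72 or 64 per group.
- *Imputed.* Let ρ be the correlation of 24-hour with 96-hour change, assumed 0.5 to 0.8. Effective n = 80 / [ρ² + (1 − ρ²)/(1 − f)]. For f = 0.10 this is 80/1.0833 = 73.8 to 80/1.04 = 76.9. For f = 0.20 it is 80/1.1875 = 67.4 to 80/1.09 = 73.4.
- *24-hour scan stands in.* Let r be the share of the effect present at 24 h, assumed 0.25 to 0.75. Expected difference = 15 × [1 − f(1 − r)]. Variance per arm = (1 − f) × 29² + f × SD24² + f(1 − f) × g². Here SD24, the SD of the 24-hour change, is assumed 15 to 29 mL. Mean growth g from 24 to 96 h is assumed 0 to 20 mL on placebo, and is g − 15(1 − r) on active. Worst case at f = 0.20 (r = 0.25, SD24 = 29, g = 20): difference 12.75 mL, variances 841 + 0.16 × 400 = 905 and 841 + 0.16 × 8.75² = 853.25, power 0.771. Best case (r = 0.75, SD24 = 15, g = 0): difference 14.25 mL, variances 717.8 and 720.05, power 0.916.

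| | f = 0.10 | f = 0.20 |
|---|---|---|
| Dropped, power | 0.869 | 0.827 |
| Imputed, power (15 mL kept) | 0.877–0.890 | 0.846–0.875 |
| Stand-in, expected difference (mL) | 13.9–14.6 | 12.8–14.3 |
| Stand-in, power | 0.844–0.909 | 0.771–0.916 |

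**4. Unequal missingness with no drug effect, stand-in reading only.** Shift = (gap in missing rates) × g. A gap of 0.05 with g = 10 mL gives 0.5 mL; a gap of 0.10 with g = 20 mL gives 2.0 mL. With SE 4.585 the rejection rates are 0.051 and 0.072 against a nominal 0.05.

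**The case against.** The omission itself has no good defence. The strongest replies concern its reach.

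**Table 1 sets a bound.** A reader might infer that the SAP has replaced imputation with an unlimited closest-read rule. The documents do not establish that. Section 3.1 maps scheduled and unscheduled efficacy data analysed by visit to Table 1, its exception clause concerns the choice among reads within a window, and 3.4.1 itself speaks of visits. This stands: the text shows an unresolved conflict, not a settled substitution.

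**Early scans can be legitimate.** The last scan before DC, IPH evacuation or CMO is part of the endpoint, and the primary objective refers to scans up to and including the 96-hour scan. Protocol Table 2, footnote 2 asks for imaging before early discharge. So not every early scan is a missing value, and that stands. It does not remove the need for imputation. The protocol's modified intention-to-treat set (16.2.1) already requires a post-baseline read, and 13.1 already picks the edema scan closest to 96 hours, yet the protocol still requires imputation for both endpoints.

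**Other outputs would show the pattern.** The separate 24-hour analysis and the by-visit summaries with counts would hint at a problem. They are not sensitivity analyses of the primary result.

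**The numbers do not favour imputation decisively.** Correct. Every input beyond the sample size assumptions is assumed, and the stand-in rule can give higher power than imputation.

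**Conclusion.** The concern holds for the undeclared removal of multiple imputation and of the missing-data sensitivity analysis. It also holds for the conflict between Table 1 and 3.4.1 with 5.6.2. Whichever rule governs, the protocol's primary and edema analyses are not carried out as written. This should be corrected before the primary analysis.

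The size is unknown. The ranges above rest on assumed missing rates, 24-hour effect, 24-hour SD, growth and correlation. Participants with a usable pre-procedure scan are not missing, so the group affected may be smaller than 10% or 20%. The blended effect and the shift under unequal missingness arise only if 3.4.1 with 5.6.2 governs.

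Two further inferences are not supported. Power does not decide for imputation: the case rests on the estimand and on following the pre-specified method. Nor is the sample size calculation in error: its stated power reproduces.

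**What to change.** 1. In SAP 3.4.1 and 5.6.2, state that the Table 1 window defines an observed Hour 96 value for participants without DC, IPH evacuation or CMO. For participants with such a procedure before 96 h, state that the last admissible pre-procedure scan is used whatever its time.
2. Restore multiple imputation for missing Hour 96 contusion and edema volume, using treatment arm, baseline, 24-hour and any intermediate reads and the stratification factors, combined by Rubin's rules. The protocol's primary ANCOVA adjusts for 96-hour imaging modality, which an imputed participant lacks, so state how it is set (for example, impute the volume at a fixed reference modality). Keep closest read as a sensitivity analysis.
3. SAP 3.4 excludes reads after early end of infusion, whereas the protocol endpoint truncates only for DC, IPH evacuation or CMO. Reconcile the two, or declare the difference in Section 6.
4. Alternatively, if the sponsor prefers closest read, declare and justify it in Section 6 before unblinding, and add multiple imputation as the promised missing-data sensitivity analysis.

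The cost is SAP wording, some programming and possibly a slightly wider interval. The SAP already plans 100 imputations and Rubin's rule for GOS-E.

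A separate minor point for the same edit: align the 10 h limits (SAP 3.6.1 and the Table 1 Hour 24 window) with the 12 h limits (SAP 5.6.2, protocol 16.2.1).
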